# Introduction

## **A1 Study Abstract**

The opioid and stimulant epidemic has resulted in widespread detrimental consequences among vulnerable populations, especially among pregnant and postpartum women and people (PPWP) with opioid use disorder (OUD) and stimulant use disorders. Although perinatal use of medication for OUD (MOUD) (previously called medication assisted treatment, MAT) within a comprehensive treatment plan is the current standard of care for those with OUD or SUD, PPWP struggling with addiction may underestimate or misjudge its benefits. In this project, we will utilize a theory-based digital therapeutic tool, uMAT-R mobile application (“app”), to educate and motivate PPWP with OUD or SUD. We will assess uMAT-R’s usability among PPWP recruited from the addiction treatment facilities. We will also educate PPWP about local recovery community centers (RCCs) and link participants to these centers, in attempt to cultivate recovery capital. Recovery capital includes personal and environmental resources, such physical and mental health, social networks and support, and motivation for recovery. RCCs are primed to help individuals acquire recovery capital and often feature voluntary, peer-led recovery focused initiatives.

With Aim #1, we will garner qualitative input from PPWP with OUD or SUD (target users) on the intervention components of uMAT-R for feedback on adaptation and implementation. Participants’ input on methods to increase participation and retention for follow-up assessments will also be obtained. We will conduct interviews with PPWP with OUD or SUD (total n= 64) recruited from addiction treatment facility, with 24 local providers who serve PPWP with OUD or SUD and/or work at local recovery community centers (RCCs). We will also collect survey and follow up interviews among PPWP participants at 1-month to further assess the usability and acceptability of this tool among PPWP to inform future evaluations of preliminary efficacy among this group. This novel technology-based intervention could be an invaluable tool to assist providers in the treatment of OUD or SUD among PPWP.

## **A2 Primary Hypothesis**

**AIM #1:** We will garner qualitative input from PPWP with OUD or SUD (target users) and local providers on the intervention components of uMAT-R for feedback on the adaptation and implementation. Participants’ input on methods to increase participation and retention for follow-up assessments will also be obtained. We will conduct interviews with PPWP with OUD or SUD (total n= 64) recruited from addiction treatment facility, and with 24 local providers who serve PPWP with OUD or SUD. We will also follow up with participants to gather additional feedback on their experiences with uMAT-R and recovery after at 1 month (survey, interview).

□ **Hypothesis:** We hypothesize that our participants will report good efficiency, technical effectiveness, and satisfaction with uMAT-R, and will provide useful feedback for app improvements.

## **A3 Purpose of the Study Protocol**

The purpose of this protocol is to outline the methods utilized in this study. As we are researching a particularly vulnerable population (PPWP) with opioid use disorder or stimulant use disorder, this protocol also details the protections we have taken to ensure the safety of our participants.

# **B Background**

## **B1 Prior Literature and Studies**

**Prevalence and Treatment of Opioid and Stimulant Misuse.** Recent trends indicate increased use of opioids and stimulants among adults, contributing to several adverse public health outcomes. Opioids are a main contributor of overdose deaths across the US. The prevalence of OUD and stimulant misuse during pregnancy is likewise increasing.

Stimulants such as methamphetamine pass through the placenta and blood brain barrier and can have significant effects on the fetus and the newborn. Opioid agonists will also cross the placental barrier in concentrations consistent with maternal dose, and may adversely affect the fetus. Additionally, the postpartum period represents a time of increased vulnerabilities, and women and people with opioid use disorder relapse far more often in the postpartum period compared to with during pregnancy.

**The Benefits of MOUD.** Perinatal use of MOUD within comprehensive treatment is the current standard of care alternatives (i.e., withdrawal or detoxification) run the risk of relapse and treatment dropout. Unfortunately, PPWP struggling with OUD may underestimate or misjudge the benefits of MOUD and/or may lack support outside of the clinic to sustain motivation for recovery; these barriers could compromise treatment compliance. For instance, common misperceptions about MOUD are that MOUD is substituting one addiction for another; MOUD is ineffective because it does not immediately cure dependence; and for PPWP with OUD, it is not well known how MOUD will affect both them and their unborn child. To supplement providers' efforts at educating patients, we will develop a digital therapeutics tool, uMAT-R, to target one's (lack of) knowledge and/or negative beliefs that may deter MOUD use. To supplement traditional in-person psychiatric care, we will also include features within uMAT-R to encourage adherence to MAT, support women and people in their everyday lives, and help keep them motivated on their path to recovery.

**The Role of RCCs.** Guided by stress and coping theory, it can be assumed that greater access to recovery capital may enable persons with OUD or SUD to be better prepared to manage life's stressors and achieve recovery. RCCs are primed to help individuals acquire recovery capital. RCCs are not aligned with a specific recovery framework, allowing for RCCs to be a part of various pathways to recovery. In the greater St. Louis area (including Missouri and nearby Illinois), more RCCs are emerging. Overall, these RCCs provide recovery support and resources in person and virtually, which allows for flexibility during the COVID-19 pandemic and for individuals who may have barriers to transportation. While there is a regional need for OUD and SUD care for PPWP, there is little knowledge on how this population transitions to the next stage in their recovery post-discharge from a structured, clinical program. In the current proposal, in addition to a focus on continued MOUD uptake/ adherence via improved MOUD attitudes and beliefs, app-based content and within app e-coaching will promote engagement in local RCC's by increasing participants' knowledge about recovery and improving their recovery capital and motivation to stay sober.

**Preliminary Study: Testing a prototype of uMAT-R.** The use of a prototype of uMAT-R that we developed in partnership with iTether (IRB ID [201706044](#)) was piloted with 29 participants with OUD. For this pilot, we recruited individuals who were socially networking about opioid abuse on social media. The features of uMAT-R were guided by SAMHSA online resources about MOUD. Our uMAT-R prototype described the cost of MOUD, presented the latest research about MOUD efficacy, and described potential side effects of MAT. Video testimonials from individuals who have had success with MOUD were also provided. Following their use of this digital therapeutic tool, feedback from participants was overwhelmingly positive. In addition,

the app increased positive attitudes about MOUD (pre-app mean score 3.31, sd 0.46; post-app mean score 3.46, sd 0.52;  $t(25)=2.12$ ,  $p=0.044$ ) and interest in starting treatment (pre-app 32%, post-app 48%; McNemar's test  $p=0.046$ ). This study demonstrates our ability to partner with iTether to develop an efficacious digital therapeutic tool that improves MOUD attitudes among individuals struggling with OUD. We will adapt the educational content of this prototype to address the concerns of PPWP who misuse opioids as well as add daily tips and tailored guidance from an online coach.

## ***B2 Rationale for this Study***

**Digital therapeutics can help to combat the opioid and stimulant epidemic.** Many individuals, including those who are struggling with substance use disorder, have interest in using apps to support their recovery; likewise, our preliminary research has shown that individuals with OUD and stimulant use disorder have also demonstrated a willingness to try digital therapeutics and that they can efficaciously improve MAT attitudes. Furthermore, digital therapeutic tools have the potential to deliver therapeutic content in an accessible and engaging modality that exists at one's disposal, encourages adherence to treatment, and delivers personalized support outside of clinical care. However, there are no known published studies that evaluate the efficacy of an app focused on supporting PPWP with OUD towards MOUD treatment adherence. To address this critical gap, we will develop and pilot test the components of uMAT-R, a digital therapy, to provide a sustainable, low-cost intervention to educate, motivate, and support OUD and SUD recovery among PPWP with OUD and/or OUD.

## **C Study Objectives**

### ***C1 Primary Aim***

To assess the feasibility of linking PPWP with the uMAT-R app as a supplement to addiction treatment and explore usability characteristics of and engagement with uMAT-R.

**Activities for Aim #1:** We will garner qualitative input from PPWP with OUD or SUD (target users) on the intervention components of uMAT-R for feedback on the adaptation and implementation. Participants' input on methods to increase participation and retention for follow-up assessments will also be obtained. We will conduct interviews with PPWP with OUD or SUD (total  $n=64$ ) recruited from addiction treatment facility and/or through referrals received from other participants and members of the community. Twenty-four local providers who treat OUD will also be recruited to provide their feedback. Guided by the International Organization for Standardization, we will assess 3 domains of usability characteristics: efficiency, technical effectiveness, and satisfaction with uMAT-R, as well as the level of engagement with the app. Using a mixed methods approach, we will explore how uMAT-R fared in regard to its ease of understanding, helpfulness, intuitive flow, presentation, and pacing.

We will also collect survey and follow up interviews among PPWP participants at 1-month to further assess the usability and acceptability of this tool among PPWP to inform future evaluations of preliminary efficacy among this group.

### ***C2 Rationale for the Selection of Outcome Measures***

This study will use a combination of quantitative and qualitative measures to examine the usability characteristics of and engagement with uMAT-R (Aim #1).

## **D Study Design**

## ***D1 Overview or Design Summary***

In this study, we will recruit 64 adult ( $\geq 18$  years) PPWP for their opioid use disorder at various addiction treatment facilities. An additional 24 local providers who treat OUD will be recruited to provide their feedback. All participants will receive access to uMAT-R. PPWP participants will complete quantitative online survey assessments at baseline and at 1 month follow up. After having access to the app for 1 week, all participants will be asked to take part in an interview to provide in-depth feedback about their experience with uMAT-R (conducted in-person or via Zoom or phone). After 1 month, PPWP participants will also be asked to take part in a follow up interview to provide additional information on their lived experience with SUDs and other recovery-related constructs. All interviews will be transcribed verbatim for qualitative analyses.

## ***D2 Subject Selection and Withdrawal***

### **2.a PPWP Inclusion Criteria**

- 1) Receiving treatment at a consenting treatment facility and/or referred from other participants or community partners
- 2) Misused opioids or stimulants at some point in their life
- 3) Pregnant (second or third trimester) or postpartum within the past three years
- 4) Adult ( $\geq 18$  years of age)
- 5) U.S. resident
- 6) Own a smartphone with an iOS or Android operating system

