### **2.a Exclusion Criteria**

- 1) Currently incarcerated

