### **2.c Subject Recruitment Plans and Consent Process**

Eligible participants (N=64) will be recruited from various addiction treatment facilities or community referrals. PPWP coming to the facility receive addiction treatment (medication + counseling), and are closely supervised (e.g., weekly visits, urine drug screens, counseling session attendance) by the medical team. The research team will meet with various groups that could be eligible for the study. We are also requesting a waiver of documented consent for participants in this study, as this study poses minimal risk, and we have systems in place to protect the confidentiality of our participants. The research team will review the informed consent document with participants via phone, and participants may provide verbal consent to take part in the study. The research team will continue to follow up with participants via phone, email, and within the app to complete necessary follow-up activities. Prospective participants who have been

referred by another participant or another community partner can reach out to our team via phone to complete the screener over the phone and can be enrolled if they are eligible. In some cases, the study team may run into the same participants at the treatment facilities. If the participant expresses interest in the study again, the participant will be asked to fill out a screener. A research team member will then check to see if the participant has accessed the uMAT-R app during their previous participation. If the participant has accessed the uMAT-R app in their previous study participation, they are not eligible to be reconsented to the study. Participants who are enrolled into the study but have yet to complete their baseline survey and log into the app will be able to be reconsented to the study as they approach their 1-week study period.

Specifically, for the CARE Clinic at Washington University School of Medicine, the research team will view their Monday afternoon clinic schedule in EPIC to see when individuals are scheduled that could be eligible for the study.

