## E Study Procedures

### *E1 Screening for Eligibility*

PPWP coming to a STR Treatment Agency, Federal Qualified Health Center, or another local substance use treatment center are provided with opiate and/or stimulant addiction treatment (counseling) and are closely supervised by their behavioral health team. The research team will meet with various groups that could be eligible for the study. A member of the research team will then go over the consent document in person or over the phone with the participant. If a client is not eligible for the intervention due to not having access to a cellphone, they will be asked if they want to complete the baseline survey. Prospective participants who have been referred by another participant or another community partner can reach out to our team via phone to complete the screener over the phone and can enrolled if they are eligible.

Specifically, for CARE Clinic at Washington University School of Medicine, the research team will view their Monday afternoon clinic schedule in EPIC to see when individuals are scheduled that could be eligible for the study.

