## **F Statistical Plan**

### ***F1 Sample Size Determination and Power***

The primary purpose of this study is feasibility. We will receive information on uMAT-R with 64 PPWP participants; this sample size is feasible to recruit from various treatment facilities, is within the range of samples sizes for other pilot tests of digital therapeutics, and is sufficient for data saturation for qualitative interviews.

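### Criterion 1 lets referred people enrol without being in treatment, yet notice of risk and handover of care are addressed outside the study only to a treatment team or facility

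*Combined protocol and SAP*

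**What the plan says.** **Eligibility.** In D2 2.a, criterion 1 for pregnant and postpartum women and people (PPWP) reads "Receiving treatment at a consenting treatment facility and/or referred from other participants or community partners". Criterion 2 is "Misused opioids or stimulants at some point in their life". The only exclusion is "Currently incarcerated".

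**Recruitment, with referral as a route of its own.** C1 describes PPWP "recruited from addiction treatment facility and/or through referrals received from other participants and members of the community". D2 2.c says that eligible participants "will be recruited from various addiction treatment facilities or community referrals". E1 adds: "Prospective participants who have been referred by another participant or another community partner can reach out to our team via phone". They are then screened by phone and enrolled if eligible.

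**Recruitment, facilities only.** D1 speaks of recruiting "PPWP for their opioid use disorder at various addiction treatment facilities". F1 says that "this sample size is feasible to recruit from various treatment facilities". The timetable in H4 also mentions enrolment from facilities only. D2 2.e and D3 3.e go further and state as fact that participants are patients of addiction treatment facilities.

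**Safety steps addressed to a facility.** Under D2 2.e, the treatment team is told if a coach conversation raises concern about injury or relapse. Under D2 2.g, if the research team judges after an adverse event that someone should leave the study, the treatment team is informed and takes over care. Under E3 3.d, potential harm disclosed in the app or surveys is passed to the facility.

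**The concern.** The eligibility rule and the safety steps rest on different populations. The steps assume that every PPWP participant has a clinical team behind them, while criterion 1 does not require one. Where a participant has no such team, staff who follow D2 2.e, D2 2.g or the disclosed-harm step of E3 3.d to the letter find an instruction with no addressee.

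What is at stake is patient safety in a group that A3 itself calls particularly vulnerable. A coach may see signs of relapse, injury or danger to someone else in a participant whom no clinic is following. A participant removed on safety grounds would be handed to a team that may not exist. No estimate, test or objective of the study depends on this point.

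**Working it through.** No figure in the plan bears on this, so the check is textual, with one bound.

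**Step 1: does referral alone suffice?** Yes. Criterion 1 joins its two halves with 'and/or'. Criterion 2 asks for lifetime misuse, not a current disorder or current care. Criteria 3 to 6 cover pregnancy or postpartum status, age, residence and smartphone. Being out of treatment is not an exclusion. C1, D2 2.c and E1 repeat the referral route, so the wording of criterion 1 is no slip. Neither D2 2.c nor E1 says that treatment status or a facility is recorded for referred people.

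**Step 2: do other sections narrow criterion 1?** No. D2 2.e and D3 3.e describe the sample and are not eligibility rules. They conflict with criterion 1 and do not limit it. D1, F1 and H4 suggest the expected source but set no condition.

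**Step 3: which safety steps work for a participant without a facility?**

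| Event | Section | Route inside the study | Outside recipient for care | Without a facility |
|---|---|---|---|---|
| Coach sees risk of injury or relapse | D2 2.e | none given in that section | treatment team | no addressee |
| Potential harm disclosed in app or surveys | E3 3.d | none given for that step | facility | no addressee |
| Removal after an adverse event | D2 2.g | participant is informed | treatment team, which takes over care | nobody named |
| Survey report of current suicidal thoughts | E3 3.d | direct call, then staff follow-up | crisis service if needed, then notice to facility | call, handoff and follow-up work; the facility notice has no addressee |
| Potential adverse event | E3 3.c | to the PI at once; evaluated within 72 hours | none needed | works |
| Concerning adverse event | F2 | to the MPIs at once; they decide what to do | none needed | works |

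Other parts that need no facility are licensed oversight of coaches and crisis-line information that coaches can give (D3 3.a), and close monitoring of coaching (E3 3.a).

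**Step 4: how many distinct gaps?** Coaching takes place by in-app messaging (D3 3.a), so the first two rows largely describe the same event. They form one function, notice of risk or harm. The handover in D2 2.g is the second. That makes two functions, not three.

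**Step 5: what does internal escalation leave uncovered?** E3 3.c and F2 apply only once something is treated as an adverse event. E3 3.c says what makes an event serious but does not say what counts as an adverse event. F2 illustrates concern by a marked change in mood or by suicidality. Relapse risk seen by a coach may or may not be read as an adverse event. If it is not, the only written instruction is the notice to the treatment team.

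**Step 6: how many participants?** Let R be the number referred and U the number both referred and untreated. Then 0 ≤ U ≤ R ≤ 64. The lower bound holds if every referred person is also a patient. The upper bound holds because no section caps referrals. The documents give nothing to narrow this range.

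**The case against.** The strongest reply is that the facility-only sentences are summary text left unchanged when referrals were added, that the study is a one-month app-and-interview study described as minimal risk (D2 2.c), and that staff are not left without direction. Much of this stands. E3 3.c and F2 send potential and concerning adverse events to the PI and MPIs whatever the participant's treatment status. The suicidality call, crisis-service handoff and staff follow-up in E3 3.d need no facility.

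A reader might infer that untreated participants have no safety net, or that staff have no written instruction to involve the MPIs. The documents say otherwise for anything handled as an adverse event. A reader might also infer that untreated people will certainly be enrolled, or in large numbers. The text shows only that they may be, and D1, F1 and H4 point to facilities as the expected source.

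Finally, the consent documents (J2) and special procedures protocols (J4) were not available, and D2 2.e says that adverse-event procedures are explained at consent. They may contain a fallback. That limits the safety claim to the protocol body, but it does not remove the contradiction between criterion 1 and D2 2.e and D3 3.e.

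Even if stale text is the whole explanation, a correction is due. If untreated referrals are intended, D2 2.e and D3 3.e are wrong. If they are not, criterion 1 is.

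**Conclusion.** The point holds as an internal contradiction with a limited safety consequence. For an eligible participant without a facility, the protocol body names no outside recipient for notice of risk or harm, and nobody to take over care after a safety removal. The remaining exposure is risk not handled as an adverse event, together with those two missing recipients. The handover matters only if the team decides to remove someone.

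The contradiction rests on plain wording and is firm. The practical gap is less certain. It assumes that at least one referred, untreated person enrols and that J2 and J4 hold no fallback procedure. The number affected is unknown, from 0 to 64, and may be zero. This should be corrected, but it does not call the design or the analysis into question.

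**What to change.** Preferred, keeping the referral route:

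- In D2 2.e and D3 3.e, replace the statement that participants are facility patients with: 'PPWP participants are either treatment-facility patients or people who came by referral and may not be in treatment.' Avoid saying that most are patients, since no figure supports it.
- Record current treatment status, and the facility if any, at screening.
- Add to D2 2.e, D2 2.g and E3 3.d: 'For a participant with no treatment facility, the research team, under MPI oversight, contacts the participant directly, makes a crisis-service handoff or treatment referral as needed (for risk to others, contacts the appropriate emergency service), and documents it.' This extends the call and handoff already used for suicidal thoughts and covers danger to third parties.

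Alternative, if all participants are meant to be patients: amend criterion 1 so that referred people must also be in current treatment.

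The preferred change costs a small amendment with IRB review, possibly a line of consent wording, one or two screener fields, and staff time for any case that arises. It adds no participants and no assessments beyond those fields. The alternative would turn away untreated referrals and could slow enrolment.
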